4.3.5 Subgroup Analysis: Interaction with Treatment

Subgroup analysis of the primary endpoint will follow the ITT principle and include all randomized patients. The purpose is to test if the effect of aCRT treatment on primary endpoint would vary by pre-specified subgroup factors including:

- Geography: US/Canada vs. International
- Age
- Gender: Males vs. Females
- QRS duration: ≤ 150 ms vs. > 150 ms
- AV conduction time: median as cutoff
- LBBB: Core Lab confirmed vs. Core Lab not confirmed
- NYHA class (in different model where NYHA class is a covariate not a stratification factor)
- HF etiology
- Renal dysfunction
- Diabetes

This analysis will be conducted by adding subgroup and its interaction with treatment into the model used for the primary analysis. The codes will be similar to:

```
PROC PHREG DATA=primary;  
  CLASS NYHA site subgroup;  
  MODEL time*event(0) = rand subgroup rand*subgroup / TIES=efron;  
  STRATA NYHA;  
  RANDOM site/dist = gamma;  
RUN;
```

The treatment by subgroup interaction effects will be tested at $\alpha=0.05$. P values will not be adjusted for multiplicity. The significance of interaction effects and confidence intervals of hazard ratios for subgroups will be presented in a Forest plot.

4.3.6 Ancillary Analysis: Covariate Adjustment and Risk Score

Subject characteristics at enrollment and baseline will be considered as covariates in an ancillary analysis. The purpose is to verify the treatment effect controlling for covariates. The ancillary analysis may only be conducted for the final report.

The subject characteristics include: from enrollment visit, gender, PR interval, QRS duration, and LVEF; from baseline form, age, physical exam status, cardiac disease classification, current HF symptoms, blood measurements, and medical history at baseline (section 4.1.1). NYHA class at enrollment will be regarded as a covariate instead, which means the corresponding model will no longer have the component for stratified Cox regression.

First, the effect of each subject characteristic on the primary endpoint will be estimated in a univariate model as follows:

```
PROC PHREG DATA=primary;
  CLASS site SubjCha; * CLASS only if SubjCha is categorical;
  MODEL time*event(0) = SubjCha / TIES=efron;
  RANDOM site/dist = gamma;
RUN;
```

Again, in this SAS PHREG procedure, event = 1 when a subject experiences a primary endpoint and event = 0 otherwise; and time to event starts from the date of randomization and ends at the date that the first event occurs for those who experience the event or the date of last documented follow-up since randomization for those who are censored; SubjCha is a specific baseline characteristic of interest.

Next, the subject characteristics that are significant in a univariate model will be included in a full model and backwards selection method will be used to determine significant predictors. After that, the treatment factor will be added into the model along with the interaction terms between treatment and possible effect modifiers such as gender, ECG Core Lab confirmed LBBB, AV conduction time, QRS, NYHA class at enrollment and MI. Backwards selection will be used to eliminate the interaction terms that are not significant. If an interaction is significant, the relevant subject characteristics need to remain in the model regardless whether their single effects being significant or not. Note the backwards selection will be performed manually because the SAS PHREG procedure ignores the SELECTION option for the frailty model analysis.

Based on the literatures^{8,9}, the following characteristics are expected in the final model: from enrollment form, gender, QRS duration, ECG Core Lab confirmed LBBB, LVEF, NYHA class, AV conduction time; from baseline form, age, BMI, SBP, rales/crackles, dyspnea, peripheral edema, HF admissions in past 6 months, creatinine, history of MI, AF, diabetes and smoking; from cardiovascular medication log, baseline diuretics dose, and ACE/ARB. If not, we might consider to add them into the final model in order to compare with the literature.

A risk score for the primary endpoint can be defined as $\mathbf{X}\beta$ with \mathbf{X} being the covariates remained in the final model.

The critical values for the treatment effect in the primary analysis (estimated cumulative α -level of approximately 0.00002, 0.00304, 0.0193 and 0.05 at the 1st, 2nd, 3rd interim and the final analysis, respectively) will not be applied to this ancillary analysis.

Multiple imputation will be used to handle missing values for the covariates in the multi-variable models. The SAS MI and MIANALYZE procedures will be used to conduct multiple imputation.

4.3.7 Determination of Patients/Data for Analysis

The primary analysis will follow the ITT principle. All randomized patients will be included in analysis, and for each patient the endpoints will be attributed to the arm that the patient was randomized to irrespective of the actual treatment that the patient received. Event dates will be entered in the analysis relative to the date of randomization (which will be time zero for the survival analysis). Patients will be censored if no primary endpoint has occurred prior to the end-of-study exit visit, or prior to the last documented follow-up visit if the patient was exited early (or in case of interim analysis).

Subgroup analysis and ancillary analysis will also follow the ITT principle and include all randomized patients. However, sensitivity analyses will only include randomized patients with ECG Core Lab confirmed LBBB and ITT principle is not applicable to the sensitivity analysis per actual aCRT programming.

4.3.8 Sample Size Methods and Assumptions

In this event driven trial, the number of events for the primary objective to be met is estimated using the SEQDESIGN procedure in SAS. This procedure¹⁰ assumes that with a total number of analysis stages K , the sequence of the standardized test statistics $\{Z_1, Z_2, \dots, Z_K\}$ has the canonical joint distribution with information levels $\{I_1, I_2, \dots, I_K\}$ for the parameter θ (the response difference between treatment arm and control arm)¹¹:

- $\{Z_1, Z_2, \dots, Z_K\}$ is multivariate normal
- $Z_k \sim N(\theta\sqrt{I_k}, 1), k = 1, 2, \dots, K$
- $\text{Cov}(Z_{k1}, Z_{k2}) = \sqrt{(I_{k1}/I_{k2})}, 1 \leq k_1 \leq k_2 \leq K$

If the test statistic is computed from data that are not from a normal distribution, then it is assumed that the test statistic is computed from a large sample such that the statistic has an approximately normal distribution. In the SEQDESIGN procedure, the MODEL=TWOSAMPLESURV option of the SAMPLESIZE statement derives the number of events based on the log-rank statistic for testing two survival distributions. The computation details can be found in SAS/STAT® 9.2 User's Guide¹².

A post-hoc analysis of the Adaptive CRF Clinical Study showed that, in patients with normal AV conduction and LBBB indicated by medical history and having intrinsic rhythm determined by device, aCRT was associated with a lower risk of HF hospitalization or death (unadjusted hazard ratio (HR) = 0.71, 95% CI: 0.40 – 1.27) and a lower risk of intervention for HF decompensation or death (unadjusted HR = 0.67, 95% CI: 0.38 – 1.17). After adjusting for renal dysfunction, QRS duration (≤ 156 vs. >156) and LVEF, the adjusted HR of aCRT was 0.83 (95% CI: 0.46 – 1.49) for HF hospitalization or death and 0.76 (95% CI: 0.43 – 1.35) for intervention for HF decompensation or death. The event-free rate at 2

years post randomization in the control arm was 73.1% for HF hospitalization or death and 70.3% for intervention for HF decompensation or death.

Based on these results and given the consideration that misdiagnosis of LBBB might weaken the beneficial effect of aCRT on HF event or death, it was assumed that the true intent-to-treat hazard ratio for aCRT ON compared to aCRT OFF is 0.82 and the event-free rate at 2 years post randomization in aCRT OFF arm is 75%. Assuming time to the first HF event or death follows an exponential distribution, the hazard of aCRT OFF arm is equal to $-\ln(0.75)/2 = 0.14384$.

The required number of HF event or death to get 90% overall study power is estimated using the following SAS SEQDESIGN procedure (also Section 5.1):

```
proc seqdesign
  boundaryscale=stdz
  errspend
  stopprob
  plots=boundary(hscale=samplesize);
;
Interim: design
  alpha = 0.05
  alt = twosided
  beta = 0.10
  stop = both
  nstages = 4
  method = errfuncobf
;
samplesize
  model = twosamplesurv
  ( nullhazard = 0.14384
    hazardratio = 0.81818
    acctime = 3.0
    foltime = 2.25
  );
run;
```

that assumes:

- Type I error rate: 0.05
- Type II error rate: 0.10, which corresponds to 90% power
- 3 equally spaced interim analyses plus the final analysis
- Hazard of aCRT OFF arm: 0.14384
- Hazard ratio of aCRT: 0.81818
- Enrollment duration: 3 years
- Follow-up duration: 2.25 years

The results (Section 5.1) show that a total of 1100 patients experiencing a primary endpoint will give 90% power to detect a reduction of the incidence of the primary endpoint at a significance level of 0.05, accounting for 3 equally spaced interim analyses and assuming a true intent-to-treat hazard ratio of 0.82 for aCRT ON compared to aCRT OFF.

With the inclusion of 2874 randomized patients enrolled over 3 years and followed for 2.3 years, 1100 events are expected when the true event-free rate of aCRT OFF arm is 75% at 2 years.

The study will randomize up to 3000 patients in order to accommodate attrition due to early exit and to accommodate the possibility of a somewhat lower control arm event rate. Through simulation (Section 1.1) it was confirmed that the study will have 90% power under the following assumptions:

- 3000 patients randomized in 3 years with a uniform rate
- Event-free rate of aCRT OFF arm is 75% at 2 years
- LBBB is not confirmed by the ECG Core Lab in 10% of patients
- aCRT hazard ratio is 0.78 in confirmed LBBB patients and 1.0 in unconfirmed patients
- Crossover rate at 2 years is 5% in aCRT ON arm and 8% in aCRT OFF arm
- Loss to follow-up rate is 5% at 2 years in each arm
- Final analysis is done when 1100 primary events are accrued

4.4 Secondary Objectives

Secondary objectives include the two components of the primary endpoint, clinical composite score, incidence of atrial fibrillation, quality of life, all-cause re-admission after a heart failure admission, and cost effectiveness for the healthcare system.

Interpretation of results will be guided by a formal multiple testing procedure to achieve strict control of the family wise error rate, also accounting for the interim analysis plan. Secondary objectives will be analyzed when the study has stopped for efficacy after an interim analysis or has reached the final analysis stage. As indicated in section 0, the cumulative α -level to be spent at the 1st, 2nd, 3rd interim analysis and final analysis for secondary objectives is 0.018, 0.031, 0.041 and 0.05, respectively, corresponding to a Pocock-type alpha-spending function. At the analysis stage when secondary objectives are analyzed, a Hommel procedure^{5,13} will be applied to the secondary objectives (excluding the cost-effectiveness objective) to correct for multiplicity based on the cumulative α -level of that stage. Secondary objectives for which the hypothesis is rejected under the adjusted significance level of the Hommel procedure will be reported as significant.

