11. STATISTICAL METHODS AND DATA ANALYSIS

11.1 General

Medtronic employed statisticians will perform the statistical analyses described in this section. Interim analyses will be performed by a Medtronic statistician other than the lead statistician for the study. The lead study statistician will be blinded to all interim analyses. All tests of treatment effects will be conducted in order to preserve an overall two-sided alpha level of 0.05 unless otherwise stated. An Intention-to-Treat analysis will be performed and will serve as the primary analysis for all objectives in this study. The Intention-to-Treat cohort will include all randomized subjects.

A Statistical Analysis Plan (SAP) will be created before the first interim analysis to specify analyses in further detail. In case the SAP deviates from this Clinical Investigation Plan (CIP), or the actual analysis deviates from CIP and/or SAP, this will be explained in the Final Report.

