11.4 Interim analysis methodology

The 3 interim analyses will follow a symmetric group sequential design using the alpha-spending methodology of Lan and DeMets¹⁷ with O'Brien-Fleming¹⁸ type boundaries. The statistical stopping rules are illustrated in the figure below.

Figure 2. Statistical stopping boundaries

The horizontal axis shows the number of events, indicating the timing of interim analyses after 275, 550, and 825 events, and the final analysis when 1100 events are accrued. If at any interim analysis the standardized Z statistic for the primary objective is in the darker blue area with solid boundary line, the DMC may advise to stop the study claiming the null hypothesis is rejected. This corresponds to a cumulative α -level of 0.00002, 0.00304, 0.0193 and 0.05 spent at the subsequent stages. If the Z Statistic is in the lighter blue area with dashed boundary line, the DMC may advise to stop the study for futility.

In case the study is stopped for efficacy after an interim analysis, the secondary objectives will be analyzed using a total significance level derived from a Pocock-type alpha-spending function. This corresponds to a cumulative α -level of 0.018, 0.031, 0.041 and 0.05 spent at the subsequent stages¹⁹.

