11.5 Secondary and ancillary objectives

Interpretation of results will be guided by a formal multiple testing procedure to achieve strict control of the family wise error rate, also accounting for the interim analysis plan. Secondary objectives will be analyzed when the study has stopped after an interim analysis or has reached the final analysis stage. A Hommel procedure^{20,21} will be applied to the secondary objectives (excluding the cost-effectiveness objective) using an overall α -level as determined by the stage in the interim analysis plan as described in section 11.4 above.

Secondary objectives for which the hypothesis is rejected under the adjusted significance level of the Hommel procedure will be reported as significant with strictly controlled family wise error $\alpha=0.05$.

Secondary objectives include the components of the primary endpoint, patient status at 6 months, the incidence of atrial fibrillation, and cost-effectiveness.

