A negative binomial model will be used to estimate and compare incidence rates of all-cause re-admissions after an HF admission. For each patient the number of hospital admissions that falls within 30 days of discharge from an HF admission (as classified by the investigator) will be determined. All patients will be included in the model, with a count of zero in case no 30-day readmissions occurred. The model will include an offset based on the total follow-up experience of all patients.

To assess cost-effectiveness of CRT devices with the aCRT algorithm relative to traditional CRT devices.

Analysis method for this objective will be defined in the Economic Analysis Plan. There will be no hypothesis test and therefore the objective will not be included in the Hommel multiple testing procedure.

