4.2 Interim Analysis Plan

[figure not shown]
Four analyses including three interim analyses and a final analysis are planned for the primary objective. The 3 interim analyses will follow a symmetric group sequential design using the alpha-spending methodology of Lan and DeMets² with O'Brien-Fleming³ type boundaries. Specifically, the cumulative alpha-spending function at the k^{th} look or analysis:

$$\alpha(t_k) = 2 - 2\Phi\left(\frac{Z_{\alpha/2}}{\sqrt{t_k}}\right)$$

where $k=1, 2, \dots, K$ and t_k is the information fraction at the k^{th} look, In the group sequential design for time-to-event endpoint, the information fraction at the k^{th} look can be defined as the cumulative count of events at the k^{th} look divided by the projected number of events at the final look.

The O'Brien-Fleming function was chosen because it conservatively preserves most of the type I error for the final analysis, and the conservation of type I error is desired due to the multiple endpoints and objectives of interest in this trial. The statistical stopping rules are illustrated in the figure below.

Figure 1: Statistical stopping boundaries

The horizontal axis shows the number of events, indicating the timing of interim analyses after 275, 550, and 825 events, and the final analysis when 1100 events are accrued. If at any interim analysis the standardized Z statistic for the primary objective is in the darker blue area with solid boundary line, the DMC may advise to stop the study claiming the null hypothesis is rejected. This corresponds to a cumulative α -level of 0.00002, 0.00304, 0.0193 and 0.05 spent at the subsequent stages (see section 5.1 “Error Spending Information” table). If the Z Statistic is in the lighter blue area with dashed boundary line, the DMC may advise to stop the study for futility.

In case the study is stopped for efficacy after an interim analysis, the secondary objectives will be analyzed using a family-wise type I error rate derived from a Pocock-type alpha-spending function. This corresponds to a cumulative α -level of 0.018, 0.031, 0.041 and 0.05 spent at the subsequent stages⁴. Hommel procedure will be used to correct for multiplicity.⁵ This will be implemented by the SAS MULTTEST procedure.

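### The seven secondary objectives can be declared significant at the final analysis even when the primary fails, so the promised overall two-sided 0.05 is not delivered across primary and secondaries

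*SAP*

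**What the plan says.** Protocol section 11.1, repeated in SAP section 4.1, makes the general promise: "All tests of treatment effects will be conducted in order to preserve an overall two-sided alpha level of 0.05 unless otherwise stated".

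The primary uses all of that level. SAP section 4.2 gives its cumulative two-sided alpha over the three interims and the final as "0.00002, 0.00304, 0.0193 and 0.05 spent at the subsequent stages".

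The secondaries have their own schedule. After an efficacy stop, "the secondary objectives will be analyzed using a family-wise type I error rate derived from a Pocock-type alpha-spending function", with cumulative levels 0.018, 0.031, 0.041 and 0.05. A Hommel procedure is applied within the family. Cost-effectiveness is left out (Protocol section 11.5.1: "There will be no hypothesis test and therefore the objective will not be included in the Hommel multiple testing procedure"), so seven tests remain.

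The trigger for testing them is in SAP section 4.4: "Secondary objectives will be analyzed when the study has stopped for efficacy after an interim analysis or has reached the final analysis stage". Protocol section 11.5 is looser: "Secondary objectives will be analyzed when the study has stopped after an interim analysis or has reached the final analysis stage". It drops the efficacy qualifier that Protocol section 11.4 contains: "In case the study is stopped for efficacy after an interim analysis, the secondary objectives will be analyzed using a total significance level".

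On reporting, Protocol section 11.5 says: "Secondary objectives for which the hypothesis is rejected under the adjusted significance level of the Hommel procedure will be reported as significant with strictly controlled" family-wise error at 0.05.

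**The concern.** At an interim, the efficacy-stop condition acts as a gate, because the secondaries open only if the primary null has been rejected. At the final analysis the only condition is having got there. No section of either document requires the primary to be rejected at that point.

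Two separate allowances of 0.05 are therefore in play under a promise of 0.05 overall. If the primary misses at 1100 events, a result on the Clinical Composite Score, atrial fibrillation or KCCQ could still be reported as significant. A reader would take it as covered by the overall level. The exposure is this combined claim, not the primary result.

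**Working it through.** **Inputs from the documents.** Four equally spaced looks (275, 550, 825 and 1100 events); the two cumulative alpha schedules above; Hommel over seven secondaries; advisory futility (SAP section 4.2; Protocol Appendix C treats the boundaries as guidelines).

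**Plan's own figures.**
- Secondary levels: 0.05 × ln(1 + (e − 1)t) at t = 0.25, 0.5, 0.75, 1 gives 0.0179, 0.0310, 0.0414, 0.05, as stated.
- Primary levels: O'Brien-Fleming-type spending at 0.025 per side, doubled, gives 0.000015, 0.00305, 0.0193, 0.05. This agrees with the plan apart from rounding per side.
- Events for 90% power at a hazard ratio of 0.81818, with futility stopping as in the SAP code: about 1100, as stated.

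**Bounds without a gate.** Two families at 0.05 each give at most 0.05 + 0.05 = 0.10. If they were independent, the figure would be 1 − 0.95² = 0.0975. Independence is a ceiling and not a realistic case, because all-cause death and HF intervention are components of the primary.

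**Simulation, common correlation.** Global null, 400,000 trials per row, all eight statistics sharing one assumed correlation, individual Hommel rejections counted. Efficacy limits on |Z| are 4.330, 2.963, 2.361 and 2.015 when futility is not enforced. With binding futility they are 4.330, 2.963, 2.356 and 1.963, with interim futility limits 0.005, 0.355 and 1.236. Monte Carlo standard error is at most √(0.097 × 0.903 / 400,000) ≈ 0.0005.

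| Correlation | Primary rejected | Primary missed, false secondary claim at final | Any false claim, futility not enforced | Any false claim, futility always followed, SAP trigger | Same, Protocol 11.5 trigger |
|---|---|---|---|---|---|
| 0 | 0.050 | 0.047 | 0.097 | 0.058 | 0.087 |
| 0.3 | 0.050 | 0.041 | 0.091 | 0.059 | 0.081 |
| 0.5 | 0.050 | 0.031 | 0.081 | 0.060 | 0.072 |
| 0.7 | 0.050 | 0.019 | 0.068 | 0.059 | 0.062 |
| 0.9 | 0.050 | 0.005 | 0.055 | 0.052 | 0.053 |

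The second and third columns refer to the case without enforced futility, and they add to the fourth up to rounding. There, the whole excess comes from trials that miss the primary and go on to test the secondaries at the final analysis. The last column takes Protocol section 11.5 literally, so that a futility stop also opens the secondaries. About 79% of null trials stop for futility when the boundary is followed.

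**Simulation, component correlations.** Correlations among primary, HF event and death were derived from an illness-death model at the rates in Protocol section 11.3.4: 85% event-free at 2 years, 4 years of accrual and 3.5 more of follow-up. Assumed: HF events are 60–80% of first events, and the death hazard is 2 to 6 times higher after an HF event, with and without frailty. This gives primary–HF 0.77–0.90, primary–death 0.45–0.80 and HF–death 0.07–0.40. Correlations involving the other five secondaries were set mainly at 0 to 0.40. The chance of any false claim is 0.081–0.090 with futility not enforced. With futility always followed it is 0.057–0.061 if the efficacy limits treat futility as binding, and 0.053–0.056 if they do not. These figures count rejection of the global Simes test; counting individual Hommel rejections lowers them by at most about 0.002.

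**With a gate on the primary.** The chance of any false claim is 0.050 in every setting. With a real primary effect and null secondaries, the gated error at the stated Pocock-type levels peaks at about 0.036 for the Hommel family and 0.037 for a single secondary.

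**The case against.** The best counter-argument is that primary and secondaries were meant as separate families. The secondaries have their own spending schedule ending at 0.05 and their own Hommel procedure, and that could be the exception which the general sentence allows for. On that reading the strict-control statement in Protocol section 11.5 is essentially accurate for the secondaries. This is a legitimate convention, but neither document says that control is separate or that the overall level exceeds 0.05. The general sentence, as written, promises the opposite.

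A related point is that the general sentence cannot be literal. SAP section 4.3.4 calls sensitivity results significant at the primary's own levels, and the ancillary hypotheses in Protocol section 5.1.3 have no readable multiplicity rule. That is fair. The gate gives 0.050 for the primary plus seven secondaries, not for every test in the plan. It shows that the general sentence is looser still; it does not rescue it.

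The Pocock-type levels are referenced to a paper whose title concerns hierarchical testing in group-sequential trials. A hierarchy may have been intended, but none is written for the final analysis.

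If every futility stop is followed, the excess is only about 0.002 to 0.011. Futility is advisory, however, and the excess does not vanish.

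Finally, Protocol section 11.5 refers back to section 11.4 for its level, which softens the wording mismatch. The two trigger sentences still differ.

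**Conclusion.** The concern holds. The plan promises an overall two-sided 0.05 and, for the primary and seven secondaries together, does not deliver it. The chance of any false claim under the global null is about 0.081–0.090 with component-based correlations and futility not enforced. It falls towards 0.055 if all endpoints are very highly correlated, and to 0.052–0.061 if every futility stop is followed. The size depends on assumed correlations and on how futility advice is handled; an excess appears in every setting examined. The primary test keeps its 0.05, and the secondary family on its own stays at about 0.05 or below. This should be fixed, but it does not threaten the primary conclusion.

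**What to change.** Choose one of two changes before results are seen.

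1. **Gate.** State in SAP sections 4.2 and 4.4 and Protocol section 11.5 that a secondary objective may be declared significant only if the two-sided primary null is rejected at that analysis. Otherwise, including after a futility stop, secondary p-values are nominal and descriptive. The gate is two-sided because the primary test is (SAP section 4.3.1). The cost is giving up confirmatory secondary claims when the primary is missed.
2. **Separate control.** Keep ungated testing, and reword Protocol section 11.1 and SAP section 4.1 to say that 0.05 is controlled for the primary and, separately, within the secondary family. The cost is giving up the overall-0.05 statement.

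Under either, name the tests that the error statement covers, since the sensitivity and ancillary tests lie outside it. Also align the trigger in Protocol section 11.5 with the efficacy-stop wording of Protocol section 11.4 and SAP sections 4.2 and 4.4. This takes a few sentences. Event count, sample size and data collection do not change.
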